13.5.2 Primary Effectiveness Analysis

Specular microscopy of the central cornea will be completed preoperatively and at Visit 5 (90 ± 14 days postop). Images will be evaluated by a masked reading center. If multiple cell densities are obtained from the reading center for each eye visit, then the available counts will be averaged by eye and visit (Preoperative, Visit 5) to produce a single value for each eye visit.

If one or more ITT Population eyes has a missing mean ECD value either at the preoperative visit or at Visit 5 (including due to a missed visit or due to discontinuation), then the missing data will be imputed as follows. Prior to analysis, 25 imputations of missing mean densities will be produced using the Markov chain Monte Carlo method and the variables investigator, treatment, preoperative value, and postoperative value.

For each observation in the imputed datasets, the ECD loss in percent at Visit 5 will be calculated for each eye at each visit as follows:

$$\text{Loss (\%)} = \frac{\text{Preoperative Cell Density} - \text{Visit 5 Cell Density}}{\text{Preoperative Cell Density}} \times 100\%$$

The means and standard errors from the imputed datasets will be combined to produce a continuous variable summary of the ECD (cells / mm^2) at each visit (Preoperative, Visit 5) and the percent loss at Visit 5 by randomized treatment assignment for the ITT Population.

Loss (%) will be modeled as a function of the fixed class variables treatment and investigator, separately by imputation. The parameter estimates will be combined to produce a one-sided upper 95% confidence limit for the difference in percent loss between the test

and comparator OVDs and a p-value for the hypothesis test for the ITT Population. If the upper confidence limit is less than 5%, then the null hypothesis of inferiority will be rejected in favor of the alternative hypothesis of non-inferiority.

If there are no ITT Population eyes with missing ECD data, then imputation will not be performed. Instead, the available data will be analyzed and summarized as described above.

Sensitivity analyses of effectiveness will include a best-case analysis, a worst-case analysis, a tipping point analysis, and a complete case analysis (which will use only subjects who have cell density measurements at every scheduled visit), and analysis using the PP Set.

Poolability across centers will be evaluated by modeling Loss (%) as a function of the fixed class variables treatment and investigator including their interaction using the available data. Poolability will be assessed by comparing the p-value for the interaction to a critical value of 0.15.

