12.3 Risk Assessment

All risks associated with the use of the DVisc40 dispersive OVD have been assessed and reduced to as low as reasonably practicable. Bausch + Lomb believe that the level of residual risk for this product is acceptable in the clinical setting where ophthalmic surgery is performed. An increase in IOP can follow anterior segment surgery in which OVDs are utilized. It is a recognized potential consequence of their use, is typically transient, and should not significantly impair ocular function or the repair of ocular tissues. A significant or prolonged increase in the IOP can cause pain or discomfort and result in permanent damage to the eye.³ To mitigate this risk, the Sponsor scheduled the first two post-surgical follow-up visits to assess IOP at 6 Hours \pm 2 hours postoperatively and at 24 Hours \pm 4 hours postoperatively. Also, IOP will be assessed at all follow-up visits. Other potential adverse effects include postoperative reactions including inflammation (iritis, hypopyon, endophthalmitis), corneal edema and corneal decompensation. Subjects will be assessed at all follow-up visits.

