Appendix A: STUDY FLOW CHART

PROCEDURE/ASSESSMENTS	Preop Visit Day -60 to Day -1	Op Visit Day 0	Postop Visit 1 ^a 6 Hours ± 2 hours Postop	Postop Visit 2 24 Hours ± 4 hours Postop	Postop Visit 3 7 Days ± 2 days Postop	Postop Visit 4 30 Days ± 7 days Postop	Postop Visit 5 90 Days ± 14 days Postop
Informed Consent	X						
Demographic Data	X						
Medical History	X						
Urine Pregnancy Test	X	X ^b			X	X	X
Eligibility Criteria	X	X					
Randomization		X					
Fellow Eye Status	X						
Surgical Procedure ^c		X					
Manifest Subjective Refraction	X						X
Uncorrected Distance VA	X		X	X	X	X	X
Best Corrected Distance VA	X						X
Cataract Classification	X						
Slit Lamp Exam	X		X	X	X	X	X
Intraocular Pressure (Goldmann tonometry)	X		X	X	X	X	X
Fundus Exam (Dilated)	X						X
Ultrasound Pachymetry	X			X			X
ECD via specular microscopy of the central cornea	X						X
Concomitant Medications	X	X	X	X	X	X	X
Adverse Events ^d	X	X	X	X	X	X	X

^a Postoperative Visit 1 must occur on the day of surgery.

^b If last urine pregnancy test was more than 21 days after the preoperative visit, test should be repeated.

^c Required details of the surgical procedure are described in [Appendix C](#).

^d The period of collection of AEs starts from informed consent through study exit

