2.0 SLIT LAMP EXAMINATION

Slit lamp examination will be performed using a slit lamp biomicroscope and observations graded per the following classifications of slit lamp observations:

Cataract Type (pre-operative)

- Nuclear
- Cortical
- Posterior sub-capsular
- Combination

Cataract Density (pre-operative)

- 1+ = Slight
- 2+ = Moderate
- 3+ = Dense
- 4+ = Very dense*

* Very dense cataract excludes subject from study

Central Corneal Stromal Edema (pre-operative and post-operative)

- None – No evidence of central corneal stromal swelling with normal transparency
- Mild – Mild central corneal stromal swelling
- Moderate – Moderate central corneal stromal swelling
- Severe – Definite widespread cloudiness or haziness giving dull ground glass appearance to cornea, or numerous coalescent bullae

Corneal Wound Edema (post-operative only)

- None – No evidence of corneal wound swelling with normal transparency
- Mild – Mild corneal wound swelling
- Moderate – Moderate corneal wound swelling
- Severe – Definite widespread cloudiness or haziness giving dull ground glass appearance to cornea, or numerous coalescent bullae

The slit lamp examination includes the measurement of aqueous cell and flare by the Standardization of Uveitis Nomenclature (SUN) Working Group grading system.⁵ For the evaluation of cells and flare, using a 1 mm x 1 mm slit beam, the following SUN grading scheme must be used:

Anterior Chamber Cells (post-operative)

Grade	Cells in Field
0	<1
0.5+	1-5
1+	6-15
2+	16-25
3+	26-50
4+	>50

Anterior Chamber Flare (post-operative)

Grade	Description
0	None
+1	Faint
+2	Moderate
+3	Marked
+4	Intense

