3.0 ECD

Specular microscopes that will be used in the study must first be certified by the central reading center prior to its use for study purposes. At least two study staff members that will be obtaining ECD images and using the specular microscope as delegated by the PI must be trained and certified by the central reading center to ensure proper and consistent imaging prior to capturing study subject images. Documentation of such training and qualifications will be maintained in the site files. The ECD technicians should be delegated as a primary or back-up technician with the primary ECD technician obtaining ECD images whenever possible and the back-up technician obtaining ECD images as necessary in lieu of the primary technician.

Clinical sites are to use their specular microscopes in accordance with the manufacturer's and reading center's recommendations and procedures. Calibration of specular microscopes will be documented and filed at each clinical site.

Standardized ECD count methods²⁸ will be used to minimize variability. The measurement of the ECD in the central cornea will be performed preoperatively and at three months postoperatively (Visit 5) at all sites using a non-contact Specular Microscope (approved by or supplied by the Sponsor). Three images from the central part of the cornea will be obtained for each applicable subject visit.

Initial eligibility determination by the sites is not dependent on receiving reading center ECD results. However, subjects with automated counts below an average of 1750 cells/mm² must await confirmation of >1500 cells/mm² from the reading center prior to enrolling the subject.

To determine ECD, sites will submit all preoperative and three month postoperative images to the reading center (which will be masked) for image analysis. The reading center will determine the mean ECD based on the three images.

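### The imputation of missing Visit 5 ECD leaves out the pachymetry and corneal oedema grades that the trial collects, so any eye that is missing because its cornea was swollen is imputed like a readable eye

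*Combined protocol and SAP*

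**What the plan says.** ECD loss at Visit 5 is the only effectiveness endpoint. Section 13.5.2 states that "Specular microscopy of the central cornea will be completed preoperatively and at Visit 5", so there is one postoperative measurement occasion. Appendix B, 3.0 adds that "Three images from the central part of the cornea will be obtained for each applicable subject visit", and the reading centre reports their mean.

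Where an ITT eye lacks a value at either visit, the gap is filled 25 times. The method and model are specified in one phrase: "using the Markov chain Monte Carlo method and the variables investigator, treatment, preoperative value, and postoperative value". Missed visits and discontinuation are named as reasons for a missing value; an ungradable image is not named. The co-primary decision uses the combined imputed result against the 5% margin. Section 13.5.3.2 reuses the same imputation and model for the ECD superiority test.

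Section 13.5.2 also lists best-case, worst-case, tipping-point, complete-case and per-protocol sensitivity analyses, without defining the first three.

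Other corneal data are collected. Appendix A schedules "Ultrasound Pachymetry" preoperatively, at 24 hours and at Visit 5, and a slit-lamp examination preoperatively and at all five postoperative visits. Appendix B, 2.0 grades central stromal oedema at that examination, with the top grade described as "Definite widespread cloudiness or haziness giving dull ground glass appearance to cornea". Section 12.3 names "corneal edema and corneal decompensation" among potential adverse effects. The analyses set out in Section 13 use neither pachymetry nor the oedema grade.

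**The concern.** The endpoint measures endothelial damage. A badly damaged endothelium may show itself as a swollen, cloudy cornea, and such a cornea may be hard to image. In that case the value is missing because of the outcome. The planned model has no postoperative information to recognise the eye: it draws the missing ECD from readable eyes of the same arm, site and baseline.

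The protocol makes an ungradable Visit 5 image worth tracking. Section 8 bars study treatment when no analysable specular image can be obtained, and Section 8.2 excludes corneal oedema and any condition that prevents reliable specular microscopy. Treated eyes should therefore be readable at baseline, so an image that cannot be graded at Visit 5 is a post-treatment event.

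If one arm has more such eyes, its mean loss is understated and the non-inferiority comparison moves in its favour. The relevant error is declaring non-inferiority when the test OVD is truly 5 points worse.

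**Working it through.** **The plan's own figure.** Section 13.3.2 gives 93.90% power for 165 per arm, margin 5, SD 14.2 and one-sided 0.05.
- SE = 14.2 × √(2/165) = 1.563.
- The noncentral t (328 df) gives 93.90%; the normal approximation gives 93.98%. The figure reproduces, and this point does not dispute it.

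**Inputs for the bias.** From the documents: SD 14.2%, 165 per arm, margin 5, one-sided 0.05. Assumed, because the documents are silent: readable control eyes lose 10% on average; failed (ungradable, oedematous) eyes truly lose L = 30% or 45%; the share of failed eyes is p_t in test and p_c in control; the true difference is exactly 5 points.

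**Formulas.**
- True control mean: C = (1 − p_c) × 10 + p_c × L.
- True test mean at the null boundary: C + 5.
- Mean of readable test eyes: m = (C + 5 − p_t × L) / (1 − p_t).
- Failed eyes are imputed like readable ones, so the estimate centres on m − 10.
- Bias = 5 − (m − 10) = 15 − m.
- False non-inferiority rate = Φ(bias/SE − 1.645).

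**One case in full (4% v 2%, L = 45).** C = 0.98 × 10 + 0.02 × 45 = 10.7. Test mean = 15.7. m = (15.7 − 1.8)/0.96 = 14.48. Bias = 0.52. Rate = Φ(0.521/1.563 − 1.645) = 9.5%.

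| Failed eyes, test v control | Bias, L = 30 to 45 (points) | False non-inferiority (nominal 5%) |
|---|---|---|
| 2% v 1% | 0.10 to 0.26 | 5.7% to 6.9% |
| 4% v 2% | 0.21 to 0.52 | 6.5% to 9.5% |
| 3% v 0% | 0.46 to 0.93 | 8.9% to 14.7% |

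**Equal frequency and severity.** With p_t = p_c = p, m − 10 = 5/(1 − p). At p = 2% this is 5.10: a shift of 0.10 points, and against the test OVD. There is essentially no bias.

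The formula holds SE at its planning value and ignores imputation variance and site effects.

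**Would auxiliary variables help?** A simulation used 184 per arm, 25 imputations, Rubin's rules and 1,500 trials per scenario, at a true difference of 5. Four test eyes and no control eyes failed, each 40 points worse than readable test eyes. This is harsher than the table.

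| Imputation model | Mean estimate (truth 5) | False non-inferiority |
|---|---|---|
| Without auxiliary variable | 4.05 | 16.0% |
| Auxiliary, correlation 0.3 with loss | 4.21 | 13.1% |
| Auxiliary, correlation 0.5 | 4.34 | 9.5% |
| Auxiliary, correlation 0.8 | 4.71 | 7.0% |

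With no failed eyes, the four set-ups gave 4.7-6.0%; the Monte Carlo standard error near 5% is √(0.05 × 0.95/1500) = 0.6 points. The simulation left out investigator, added 5% random missingness, and assumed baseline ECD of mean 2500 and SD 300 with 10% typical loss. It shows direction and rough size only.

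**The case against.** **The mechanism is inferred.** Nothing in the documents says that oedema makes a Visit 5 image ungradable, or how often. The oedema wording in Appendix B is one category of a grading scale, and Section 12.3 speaks of potential effects, not expected ones. The exclusions for corneal pathology, previous corneal surgery, baseline ECD below 1500 and grade 4+ nuclear cataract remove many eyes at risk. All of this stands, and is why the point is conditional.

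**One image or three.** A reader might infer that the endpoint hangs on a single image. It hangs on a single visit with three images, and Section 13.5.2 averages the available counts. The value is missing only if none can be graded. All three show the same central cornea, however, so diffuse swelling could affect them together.

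**Direction.** A reader might infer that the plan is biased toward the test OVD. It is not so by construction: the bias favours whichever arm has more failed eyes. The effect on the superiority test is less clear still and has not been quantified. At its null of equal mean loss, extra failures in the test arm would have to be offset by better results in its readable eyes.

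**Size.** A tempting shortcut multiplies the difference in failure rates by failed-eye loss minus 10%, which gives 0.4-0.7 points for 4% v 2%. That uses the same typical loss in both arms while assuming a true 5-point difference, which is inconsistent. The working above keeps the true difference at 5 and gives 0.21-0.52.

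**Existing safeguards.** Worst-case and tipping-point analyses do probe non-random missingness, so the plan does not ignore it. But they are undefined and play no part in the success decision, and the complete-case analysis drops the same eyes. Section 13 leaves further detail to the SAP, so their definition may be pending.

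**Conclusion.** The concern holds in conditional form. The ECD imputation omits two measures of corneal state that the trial collects, and if Visit 5 values are missing through corneal swelling, the co-primary comparison is tilted toward the arm with more such eyes.

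Under the stated assumptions the false non-inferiority rate is modestly raised when failures are few and present in both arms, and reaches 8.9-14.7% only with 3% v 0%. The failure rates and losses are illustrations, not estimates. The documents do not show that the problem will occur. As planned, though, a reader of the results could not tell whether it had, because no count of ungradable Visit 5 values by arm is specified. The improvement is worth making because it is cheap and uses data already collected.

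**What to change.** In Section 13.5.2, or in the SAP before database lock:

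1. Add to the ECD imputation model, as auxiliary variables, the change in pachymetry from preoperative to 24 hours and to Visit 5, and the postoperative central stromal oedema grade. Keep investigator, treatment and preoperative ECD.
2. Report by arm the number of Visit 5 ECD values missing because images were ungradable, separately from missed visits.
3. Define the planned tipping-point analysis so that it shifts the imputed losses of eyes missing with oedema or ungradable images.

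The cost is SAP wording, a slightly larger model and one extra table, with no new visits or measurements. There are limits. Visit 5 auxiliaries are absent when the visit itself is missed, so only the 24-hour pachymetry and earlier oedema grades help those eyes. The relation between the auxiliaries and ECD is learned from readable eyes and extrapolated to ungradable ones. Some bias therefore remains, which is why the third step is needed.

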7.1 Overall Study Design and Plan Description

This will be a multicenter, controlled, randomized, monocular trial of Bausch & Lomb DVisc40 (test) OVD compared to the currently marketed Alcon VISCOAT[®] (control) OVD.

Subjects scheduled to undergo cataract surgery by phacoemulsification and implantation of a posterior chamber intraocular lens (IOL) will be screened for eligibility. Subjects will be examined preoperatively to obtain a medical history, to establish a baseline for ocular condition, including ECD, and to determine eligibility. Only one eye of each subject will be included in the study. In the event that both eyes are eligible to participate in the study, the selection of the study eye will be left to the Investigator's discretion. At the time of surgery, subjects will be randomly assigned to either of the OVD groups based upon a predetermined randomization scheme. Randomization will be by a 1:1 schema (DVisc40:VISCOAT[®]) and will be stratified by site, age group and cataract severity. A method other than stratification may be employed to balance randomization. If so, the method will be specified in the statistical analysis plan (SAP).

Postoperatively, subjects will undergo ophthalmic examinations at regular intervals per the study visit schedule (refer to [Appendix A](#)). The Investigator will provide standardized pre-, intra-, and postoperative care for all study subjects at his/her site (refer to Section 11 for additional information). A delegated examiner at each site who is masked to the randomized assignment of each subject will perform all postoperative assessments.

The VISCOAT[®] OVD was chosen as the control because the product has been used in cataract surgery for over 20 years and has a proven record for safety. In addition, VISCOAT[®] OVD is classified as a dispersive OVD as is the DVisc40 OVD.

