9.1.2 Randomization Method

Subjects will be randomly assigned to one of the two OVD materials according to the randomization scheme to be provided in a computer-generated randomization code by a biostatistician otherwise not involved with the study.

Interactive Response Technology (IRT) will be utilized for randomization in this study. Randomization will be stratified by site, age group and cataract severity. A method other than stratification may be employed to balance randomization. If so, the method will be specified in the SAP. The randomization codes will be established in blocks such that approximately the same number of subjects will be assigned to the DVisc40 OVD or VISCOAT® OVD treatment groups at each site.

Subjects will be randomized to 1 of 2 treatment groups in a ratio of 1:1 (DVisc40:VISCOAT®). Each screened subject will be assigned a unique 5-digit subject number assigned by the site accessing the IRT system. The subject number assigned by the IRT system will consist of the 2-digit investigational center/site number (pre-assigned by Sponsor or its designee) and the 3-digit chronological screening order number starting with 001 (e.g. 01-001, 01-002). The study device kit will be assigned to subjects based on a randomization code and the kit will be dispensed to the subjects at Day 0 (Operative Visit) by the IRT system. The assigned kit number should be recorded in the subject's source documents and applicable case report form. A study device log will document the inventory and dispensing of study device at each investigational center.

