13.3.2 ECD Loss

The standard deviation of the ECD loss percentage with VISCOAT® is estimated to be 14.2%.²⁴ When the sample size in each group is 165 subjects, a two group 0.050 one-sided t-test will have 93.90% power to reject the null hypothesis that the test is inferior to the control (the difference in means, $\mu_t - \mu_c$, is 5% or greater) in favor of the alternative hypothesis that the test is non-inferior to the control (the difference in means, $\mu_t - \mu_c$, is less than 5%), assuming that the expected difference in means is 0% and the common standard deviation is 14.2%.

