13.3.4.2 Secondary Effectiveness Hypothesis Test: ECD Loss

A sample size of 165 in each group will have 80% power to detect a difference in means of 4.393 % assuming that the common standard deviation is 14.2 % using a two-group t-test with a 0.025 one-sided significance level.

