13.5.3.2 Secondary Effectiveness Analysis

The null hypothesis of no difference between treatment groups in ECD loss will be tested for the ITT set using the multiple imputation method and statistical model described above for the primary effectiveness analysis. A two-sided 95% confidence interval will be constructed around the difference between groups. If the null hypothesis is rejected then statistical superiority will be claimed for the test OVD in this endpoint.

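### The ECD model leaves out the age and cataract-severity strata and baseline ECD, giving up some precision if these are prognostic

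*Combined protocol and SAP*

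**What the plan says.** Section 13.5.2 specifies the primary effectiveness model: "Loss (%) will be modeled as a function of the fixed class variables treatment and investigator, separately by imputation". Estimates are pooled over 25 imputations, and the one-sided upper 95% limit for test minus control is compared with 5%. Section 13.5.3.2 tests ECD superiority "using the multiple imputation method and statistical model described above for the primary effectiveness analysis", so the same two terms serve there.

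On allocation, section 9.1.2 states: "Randomization will be stratified by site, age group and cataract severity". Sections 7.1 and 9.1.2 both add a proviso: "A method other than stratification may be employed to balance randomization". In that case the SAP is to name the method.

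Preoperative ECD appears twice in section 13.5.2. It is the denominator of percent loss, and it is in the imputation model, which uses "the variables investigator, treatment, preoperative value, and postoperative value". It is not a covariate in the analysis model. By contrast, the model for change in IOP (section 13.5.3.1.2) does adjust for baseline IOP.

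For sample size, section 13.3.2 obtains 93.90% power with 165 eyes per arm, "assuming that the expected difference in means is 0% and the common standard deviation is 14.2" percent. Section 13.3.4.2 gives the superiority test 80% "power to detect a difference in means of 4.393" percent. Section 13 leaves further detail to the SAP; the supplied text contains nothing that alters this model.

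**The concern.** Age group and cataract severity were judged important enough to balance, and baseline ECD important enough to use in imputation, but none of them reduces the residual variance in the analysis. Site alone is carried through, by way of investigator. None of the ECD sensitivity analyses listed in section 13.5.2 is described as covariate-adjusted.

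If these variables predict percent loss, two things follow. First, the upper limit compared with 5% is wider than the same data could give. Second, if the strata are also balanced by design, the planned standard error ignores that balance and the test runs somewhat below its nominal 5%.

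The ECD result matters twice. It is one of two primary endpoints that must both succeed (section 13.7.3). Its superiority test is also the only member of Family 1, on which all three Family 2 claims depend (section 13.5.3).

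**Working it through.** **Inputs.** 165 eyes per arm, SD 14.2, margin 5, true difference 0, one-sided 0.05 (section 13.3.2); one-sided 0.025 for superiority (section 13.3.4.2). The documents give no figure for how much variance the omitted variables explain, so R² (the share beyond treatment and investigator) is assumed at 0, 0.05, 0.10 and 0.15.

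**Step 1: the plan's own figures.** SE = 14.2 × √(2/165) = 1.563. Noncentrality = 5/1.563 = 3.198. The noncentral t with 328 df gives power 93.90%, as stated. The superiority difference with 80% power is 4.393, as stated. The product 95.17% × 93.90% = 89.36% also reproduces.

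**Step 2: with adjustment, by formula.** Residual SD = 14.2 × √(1 − R²). Half-width = t(0.95; 328) × SD × √(2/165). Detectable difference = 4.393 × √(1 − R²). Equivalent unadjusted total = 330/(1 − R²).

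| R² | Residual SD | Non-inferiority power | Half-width | Detectable difference (superiority, 80%) | Equivalent unadjusted eyes |
|---|---|---|---|---|---|
| 0 | 14.20 | 93.9% | 2.58 | 4.39 | 330 |
| 0.05 | 13.84 | 94.8% | 2.51 | 4.28 | 347 |
| 0.10 | 13.47 | 95.7% | 2.45 | 4.17 | 367 |
| 0.15 | 13.09 | 96.5% | 2.38 | 4.05 | 388 |

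Superiority power at a true difference of 4.393 rises from 80% to 82.0%, 84.0% and 86.0%. At R² = 0.10 the joint power becomes 95.17% × 95.72% = 91.1%.

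**Step 3: type I error if the strata are ideally balanced and omitted.** The planned critical value is in effect multiplied by 14.2/(residual SD). Alpha becomes 0.046, 0.042 and 0.037 at R² = 0.05, 0.10 and 0.15.

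**Step 4: simulation with sparse strata.** The set-up is 330 eyes, 18 sites, and 2 age and 3 severity levels (both assumed). That makes 108 cells, with permuted blocks of 4 within cell and 10,000 trials per setting. Monte Carlo SE is about 0.25 points for power and 0.002 for alpha. Planned model: treatment and site. Adjusted model: plus age group, severity and baseline ECD.

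| Source of R² | R² | Power, planned | Power, adjusted | Alpha, planned | Alpha, adjusted |
|---|---|---|---|---|---|
| None | 0 | 93.6% | 93.4% | – | – |
| Age and severity | 0.05 | 93.8% | 94.4% | 0.048 | 0.051 |
| Age and severity | 0.10 | 94.0% | 95.2% | 0.045 | 0.050 |
| Age and severity | 0.15 | 94.5% | 96.2% | 0.041 | 0.052 |
| Baseline ECD | 0.05 | 93.3% | 94.1% | 0.054 | 0.053 |
| Baseline ECD | 0.10 | 93.4% | 95.2% | 0.050 | 0.051 |
| Baseline ECD | 0.15 | 93.5% | 96.1% | 0.052 | 0.053 |
| Age and severity, blocks within site only | 0.10 | 94.0% | 95.7% | 0.050 | 0.050 |

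Simulated planned power is slightly below the formula because treatment is not exactly balanced within site. A second simulation at R² = 0.10 agreed: about 94.3% against 95.3% for the strata, and 93.9% against 95.4% for baseline ECD. It showed a loss of about 0.4 points at R² = 0, within Monte Carlo error.

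**Step 5: degrees of freedom.** With 330 eyes and 18 sites the planned model leaves 330 − 1 − 1 − 17 = 311. Adding one age term, two severity terms and baseline ECD leaves 307 (306 with one more category).

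**The case against.** The strongest reply is that nothing is broken. The model is prespecified and valid, and the sample size was set without adjustment. Any effect of leaving out balanced strata is conservative, which is the safe direction for non-inferiority. All of that stands.

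The gain also depends on an R² that the documents do not supply. Eligibility narrows two of the variables, since grade 4+ nuclear density and baseline ECD below 1500 are excluded. At R² = 0.05 the simulated power gain is only 0.6 to 0.8 points. The plan expects a 0% difference, so the benefit for superiority is a smaller detectable difference, not more power at an expected effect. These points limit the size but do not remove the gain.

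Balance on age and severity may be weak. At 330/108 cells there are about 3 eyes per cell, and another balancing method may be used. With balance by site only, alpha returns to 0.050. So the conservatism is conditional, but the precision gain is not: in that setting power still rises from 94.0% to 95.7%.

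Percent loss is already scaled by preoperative ECD. Scaling is not covariate adjustment, because any relation between baseline and percent loss stays in the residual.

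Finally, the simulation uses 330 complete eyes, whereas the planned analysis takes all randomized eyes (target 368) with multiple imputation. The figures should be read as approximate.

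**Conclusion.** The concern holds as an efficiency point of modest size. The stated power, the sample size and the validity of the test are unaffected. Under an assumed R² of 0.05 to 0.15, the formula gain is about 0.9 to 2.6 points of non-inferiority power and 0.07 to 0.20 percentage points in half-width; the simulated power gain is 0.6 to 2.6 points. At R² = 0.10, adjustment is worth about 37 additional unadjusted eyes (367 − 330). If none of the variables is prognostic, the simulated cost is about 0.2 power points, within Monte Carlo error.

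The mildly conservative alpha arises only if age group and severity are both prognostic and actually balanced. Leaving out baseline ECD costs precision alone. Because the possible loss is so small, the change should be made, although the trial does not depend on it.

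**What to change.** In each imputed dataset, model percent loss on treatment, investigator, age group and cataract severity as coded for randomization, and continuous baseline ECD. If another balancing method is adopted, use the factors it balances. Apply the same model in section 13.5.3.2, add age group and severity to the ECD imputation model, and keep the current two-term model as a sensitivity analysis. Fix all of this before unmasking, and state the age cut points and how the cataract density grades in Appendix B map to the severity categories, since the model needs both.

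No data collection changes: age, cataract classification and ECD are already recorded preoperatively (Appendix A). The model and the imputation variables are written into protocol section 13.5.2, so that section must be revised along with the SAP. Sections 15 and 15.2 require IRB/EC approval of protocol amendments before implementation. The statistical cost is about 4 to 5 of 311 residual degrees of freedom.
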